10.6 Appendix 6: Renal safety monitoring

Once a participant is exposed to study treatment, the following two categories of abnormal renal laboratory alert values should be assessed during the study period:

- Serum creatinine increase $\geq 25\%$ compared to baseline during normal hydration status
- Any one of the following:
 - Urine protein-creatinine ratio (PCR) $\geq 1\text{g/g}$ or $\geq 100\text{ mg/mmol}$, OR
 - New onset dipstick proteinuria $\geq 3+$, OR
 - New onset dipstick hematuria $\geq 3+$ (after excluding menstruation, UTI, extreme exercise, or trauma)

Abnormal renal event findings must be confirmed after ≥ 24 hours but ≤ 5 days after first assessment

Once a participant is exposed to study treatment, renal laboratory alerts or renal safety events should be monitored and followed up by the Investigator or designated trial staff.

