### 2.7.3 Laboratory data

Laboratory data consists of hematology, biochemistry, and urinalysis measurements. Observed value, absolute change, and percent change from baseline in continuous laboratory parameters will be summarized descriptively by visit and by treatment group. Frequency table of results for categorical laboratory parameters will be presented by visit. For some parameters, only screen tests are planned. Thus, summaries of post-baseline values will not be provided. For core part analyses, the summary tables will include Day 1 visit up to Day 180 visit. For final analyses, the summary table will include Day 1 visit up to Day 360 visit.

Shift tables using the low, normal, or high classification based on the normal range will be used to compare baseline to the worst post-baseline value by treatment group and study part for hematology and biochemistry measurements. All data collected after first dose of study treatment, from scheduled, unscheduled, and premature discontinuation visits will be used. For some parameters, if only screen tests are planned and there are no scheduled post-baseline values, then the shift table will not be provided. In final analyses, OLS will be used for the shift tables of extension part data. Besides, shift tables for overall study will also be provided using SAF.

The following ranges will be used for shift tables of eGFR, fasting glucose and HbA1c

- For eGFR, the categories will be:  
Severe =  $<30 \text{ mL/min}/1.73\text{m}^2$ ;  
Moderate =  $\geq 30 \text{ to } <60 \text{ mL/min}/1.73\text{m}^2$ ;  
Mild =  $\geq 60 \text{ to } <90 \text{ mL/min}/1.73\text{m}^2$ ;  
Normal =  $\geq 90 \text{ mL/min}/1.73\text{m}^2$ .
- For fasting glucose, the categories will be  $< 100 \text{ mg/dL}$ ,  $\geq 100 \text{ mg/dL}$  to  $< 126 \text{ mg/dL}$ , and  $\geq 126 \text{ mg/dL}$ .
- For HbA1c, the categories will be  $<5.7\%$ ,  $\geq 5.7\%$  to  $<6.5\%$ , and  $\geq 6.5\%$ .

For selected laboratory tests, the number and percentage of patients meeting the clinically notable criteria at any time, considering all data collected after first dose of study treatment, from scheduled, unscheduled, and premature discontinuation visits, will be summarized by

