laboratory parameter and treatment group and study part. The worst post-baseline value will be used for this analysis. In final analyses, OLS will be used for the summary of worst post-baseline value from extension part. Besides, such summary of worst post-baseline from overall study will also be provided using SAF. Notable criteria are defined in [Appendix 5.3](#). Clinically notable criteria will be considered to be met when both of the following occur:

- Post-baseline value meets the thresholds listed in [Appendix 5.3](#).
- Baseline value and any prior post-baseline values do not meet the thresholds listed in [Appendix 5.3](#).

Furthermore, the number and percentage of participants meeting notable criteria in liver function tests (LFT) will be summarized by treatment group and study part considering post-baseline data from scheduled, unscheduled, and premature discontinuation visit. LFT criteria are defined in [Appendix 5.3](#). In final analyses, OLS will be used for the summary of post-baseline value from extension part. Besides, such summary of post-baseline from overall study will also be provided using SAF.

All laboratory data will be listed by treatment group, participant, and visit/date and if ranges are available, abnormalities will be flagged.

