**Table 5-1 Clinically notable laboratory abnormalities for selected tests**

HbA1c criteria is explicitly stated in the table below.

All other criteria are met when both of the following occur:

- Post-baseline values meet the thresholds below
- Baseline values or any previous post-baseline values do not meet the thresholds below

Parameters	Criteria
Hemoglobin	$\leq 10 \text{ g/dL}$
Hematocrit	$\leq 0.8 \times \text{LLN}$
WBC(total)	$\leq 2.8 \times 10^3 / \mu\text{L}$ , $\geq 16 \times 10^3 / \mu\text{L}$

Parameters	Criteria
Platelet count	$\leq 75 \times 10^3 / \mu\text{L}$ , $\geq 700 \times 10^3 / \mu\text{L}$
HbA1c	$\geq 6.5\%$ and $\geq 0.5\%$ increase from baseline
Creatinine	$> 2 \text{ mg/dL}$
CK	$> 1$ and $\leq 3 \times \text{ULN}$
CK	$> 3$ and $\leq 5 \times \text{ULN}$
CK	$> 5$ and $\leq 10 \times \text{ULN}$
CK	$> 10 \times \text{ULN}$

Notable liver function test criteria are defined in [Table 5-2](#).

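### No planned table counts the protocol's baseline-relative renal alerts: the only renal row in SAP Table 5-1 is creatinine above 2 mg/dL, which most creatinine alerts would not reach at the baselines assumed here

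*Protocol*

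**What the plan says.** Protocol 10.6 (Appendix 6) states that, after exposure, "the following two categories of abnormal renal laboratory alert values should be assessed during the study period". The first category is a serum creatinine rise of at least 25% "compared to baseline during normal hydration status". The second is any one of a urine protein-creatinine ratio of at least 1 g/g (or 100 mg/mmol), new-onset dipstick proteinuria of 3+ or more, and new-onset dipstick hematuria of 3+ or more after stated exclusions. A repeat is required: "Abnormal renal event findings must be confirmed after" at least 24 hours and no more than 5 days. Sites then monitor and follow up.

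SAP 5.3, Table 5-1, lists the clinically notable criteria to be counted. Its one renal criterion is creatinine above 2 mg/dL. It has no urine criterion. Under SAP 2.7.3 a value counts only if "Baseline value and any prior post-baseline values do not meet the thresholds listed in" Appendix 5.3.

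Other SAP 2.7.3 outputs bear on renal change:
- absolute and percent change from baseline by visit;
- low/normal/high shifts to the worst post-baseline value for hematology and biochemistry;
- an eGFR shift in four bands (<30, 30 to <60, 60 to <90, ≥90);
- for categorical tests such as dipstick, "Frequency table of results for categorical laboratory parameters will be presented by visit";
- full listings.

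Protocol 9.4.2 promises counts of participants meeting clinically significant laboratory criteria, by group and part. Protocol 8.4.4 refers to 10.3.1 for notable values, and that section contains no numeric limits.

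**The concern.** The protocol judges renal change against the participant's own baseline. The SAP's count uses one absolute limit. In a population with mostly ordinary creatinine, the two rules pick out very different participants.

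Safety laboratory values are a secondary endpoint, compared with placebo during the core part. If the renal row is empty or nearly empty in both arms, a reader could take it as evidence against a renal effect when the row was too insensitive to show one. Meanwhile the findings that sites must confirm and follow would have no headcount by arm.

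**Working it through.** The plan states no figure for the share of alerts its table captures, so there is none to reproduce. The check compares two thresholds.

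**Inputs from the documents.** Alert: creatinine ≥ 1.25 × baseline (Protocol 10.6). SAP row: creatinine > 2.0 mg/dL with baseline not already above 2.0 (SAP Table 5-1 and 2.7.3).

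**Break-even baseline.** 1.25 × b = 2.0 gives b = 2.0 / 1.25 = 1.6 mg/dL.

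**Rise needed to exceed 2.0 mg/dL.** 2.0 / b − 1:

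| Baseline (mg/dL) | Alert met at | Rise needed for SAP row |
|---|---|---|
| 0.6 | 0.75 | more than 233% |
| 0.8 | 1.00 | more than 150% |
| 1.0 | 1.25 | more than 100% |
| 1.2 | 1.50 | more than 67% |
| 1.4 | 1.75 | more than 43% |
| 1.6 | 2.00 | more than 25% |

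Above 1.6 and up to 2.0 every alert is counted, and some smaller rises are too. Above 2.0 none is counted, because baseline already meets the limit.

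**Share of creatinine alerts not counted (assumptions).** The documents give no baseline creatinine distribution. A simulation assumed lognormal baselines (log-SD 0.2 or 0.3) and a lognormal ratio of worst value to baseline (log-mean 0.03; log-SD 0.12, 0.2 or 0.3):

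| Assumed median baseline (mg/dL) | Alerts not counted |
|---|---|
| 0.7 | 97% to nearly 100% |
| 0.8 | 94% to 99.9% |
| 0.9 | 88% to 99% |
| 1.0 | 82% to 98% |
| 1.2 | 68% to 88% |

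Urine alerts have no row in Table 5-1 at any baseline.

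**Do other outputs supply the count?**
- *Percent change.* SAP 2.1 gives mean, SD, median, quartiles, minimum and maximum. A maximum of 25% or more shows that someone rose that far at that visit, but not how many did. SAP 2.1.1 excludes unscheduled samples from by-visit summaries.
- *Creatinine shift.* A 25% rise within the normal range does not register.
- *eGFR shift.* If eGFR moves inversely with creatinine (assumption), a 25% rise multiplies it by 1 / 1.25 = 0.8. It crosses a band from baselines of 90 to below 112.5, 60 to below 75, and 30 to below 37.5. From 85 it falls to 68 and stays in its band.
- *Urinalysis.* The schedule has screening, Day 180 and Day 360, so one planned post-baseline sample per part. The by-visit frequencies come close to a per-participant count, but they omit unscheduled samples and do not link to baseline, so new onset is not derived.
- *Adverse events.* Protocol 8.6.1 makes a laboratory abnormality an AE only if it causes signs or symptoms, is judged clinically significant, or needs therapy.
- *Listings.* They show individual values and give no comparison of arms.

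**The case against.** The strongest reply is that nothing is broken. Section 10.6 tells investigators what to assess, confirm and follow; it does not say what to tabulate. For notable values the protocol refers to 10.3.1 and not to 10.6. The liver limits follow the same pattern: for participants with abnormal baseline transaminases, Protocol Table 10-1 uses more than 3 × baseline or 300 U/L, and SAP Table 5-2 uses more than 3 × baseline or 8 × ULN. Renal events are not among the SAP's events of special interest, and the protocol's background reports no increased risk of renal dysfunction. Rows built on laboratory values alone would also drop the hydration condition, the confirmation and the hematuria exclusions. At a baseline of 0.6 mg/dL, a single rise of 0.15 mg/dL would count.

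Much of this stands. A reader might infer that the SAP contradicts the protocol; it does not. A reader might also infer that renal changes are never compared between arms. That is wrong too: the percent-change summaries, shift tables, adverse event tables and by-visit urinalysis frequencies are all presented by treatment group or allow a partial view.

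What the reply does not supply is the count. The liver comparison also helps the point, since SAP Table 5-2 tabulates baseline-relative liver criteria and the HbA1c row of Table 5-1 includes a change from baseline. The renal alerts have no such counterpart, and SAP section 4 records no reason.

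**Conclusion.** The point holds as a reporting gap that is cheap to close. It does not touch the primary analysis.

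Below a baseline of 1.6 mg/dL, the SAP's creatinine row is stricter than the protocol's alert. Under assumed baselines of 0.6 to 1.2 mg/dL it needs a rise of more than 67% to 233%, so most creatinine alerts would go uncounted there. It is tempting to say almost all. That fits an assumed median of 0.7 to 0.8 mg/dL, but the simulated share falls to 68% to 88% at 1.2, and participants with eGFR down to 30 are eligible. The documents do not support a firmer figure.

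No planned output gives the number of participants per arm with a creatinine rise of at least 25% or a new-onset dipstick result of 3+ or more. That conclusion rests on the text of the SAP and not on the assumed baselines.

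**What to change.** Keep the row for creatinine above 2 mg/dL. Add to SAP Table 5-1, by treatment group and study part, using all scheduled and unscheduled post-baseline data:
1. creatinine increase of at least 25% from baseline;
2. new-onset dipstick protein of 3+ or more;
3. new-onset dipstick blood of 3+ or more.

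State with the rows that:
- any single qualifying value counts, with confirmed values shown separately where a repeat exists;
- hydration status and the hematuria exclusions are not applied, so the rows approximate the 10.6 alerts;
- core-part rows added after core-part unblinding are post hoc;
- the protein-creatinine ratio has no row, because the renal follow-up tests in Protocol Table 8-1 list an albumin:creatinine ratio instead.

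In the same edit, reconcile the new-onset condition: SAP 2.7.3 joins baseline and earlier post-baseline values with *and*, while Table 5-1 uses *or*.

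The cost is three table rows from central-laboratory data already collected. The 25% row will carry some noise, for example from hydration. Concurrent placebo participants help to calibrate it in the core part only, because both groups are on inclisiran therapy in the extension. The protocol's alert limits and site procedures stay as they are.

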10.7 Appendix 7: Diagnostic Criteria for Low or Moderated ASCVD risk

Diagnosis of low or moderate ASCVD risk in this study follows the ASCVD Risk Assessment Flowchart recommended by 2016 Chinese Guideline for the Management of Dyslipidemia in Adults (Zhao et al 2016) .

Table 10-4 ASCVD Risk Assessment Flowchart

Those who meet any of the following conditions can be directly classified as Very High Risk or High Risk: Very High Risk: Established ASCVD High Risk: 1) $\text{LDL-C} \geq 4.9\text{ mmol/L}$ or $\text{TC} \geq 7.2\text{ mmol/L}$ 2) Diabetes patients over 40 years old with $1.8\text{ mmol/L} \leq \text{LDL-C} < 4.9\text{ mmol/L}$ (or) $3.1\text{ mmol/L} \leq \text{TC} < 7.2\text{ mmol/L}$			
If not meet above condition, need to further assess 10-year ASCVD risk as follows.			
No. of Risk Factors*	Serum Cholesterol Level Classification (mmol/L)		
	3.1 $\leq \text{TC} < 4.1$ (or) 1.8 $\leq \text{LDL-C} < 2.6$	4.1 $\leq \text{TC} < 5.2$ (or) 2.6 $\leq \text{LDL-C} < 3.4$	5.2 $\leq \text{TC} < 7.2$ (or) 3.4 $\leq \text{LDL-C} < 4.9$
Without hypertension 0~1	Low Risk	Low Risk	Low Risk
2	Low Risk	Low Risk	Moderate Risk
3	Low Risk	Moderate Risk	Moderate Risk
With hypertension 0	Low Risk	Low Risk	Low Risk
1	Low Risk	Moderate Risk	Moderate Risk
2	Moderate Risk	High Risk	High Risk
3	High Risk	High Risk	High Risk
For Moderate Risk patients under 55 years old, assess lifetime residual risk			

 • Those who meet any 2 of the following risk factors can be classified as High Risk: $\text{SBP} \geq 160\text{ mmHg}$ or $\text{DBP} \geq 100\text{ mmHg}$ $\text{Non-HDL-C} \geq 5.2\text{ mmol/L}$ (200 mg/dL) $\text{HDL-C} < 1.0\text{ mmol/L}$ (40 mg/dL) 			

BMI \geq 28 kg/m²
Smoking

*Risk Factors: Smoking, low HDL-C, Male \geq 45 years old or Female \geq 55 years old

11 References

References are available upon request

**Document History – Changes compared to previous final version of SAP**

Date	Time point	Reason for update	Outcome for update	Section and title impacted (Current)
19-June-2023	Prior to core part DB lock		N/A - First version	NA
22-April-2024	Prior to core part DB lock		SAP Amendment 1	Section 2.2.1 Section 2.5.6
				Section 2.3.2
				Section 2.4.2
				Section 2.7.1
				Section 2.7.1.1
				[REDACTED]
				Appendix 5.1.3

Date	Time point	Reason for update	Outcome for update	Section and title impacted (Current)
21-August-2024	Prior to final DB lock		SAP Amendment 2	Section 2.2 Section 2.3.1 Section 2.4.1 Section 2.4.2 Section 2.7 Section 2.8 Appendix 5.5
				Section 2.4 Section 2.7.1 Section 2.8
				Section 2.7.3
				Section 2.4.1
				Section 2.7.1 Section 2.7.1.1

Date	Time point	Reason for update	Outcome for update	Section and title impacted (Current)
				Section 2.7.1
				Section 2.3.1
				Section 5.4.2

**List of abbreviations**

AE	Adverse Event
AESI	Adverse Event of Special Interest
AGB	ADaM Governance Board
ALP	Alkaline Phosphatase
ALT	Alanine Aminotransferase
ANCOVA	Analysis of Covariance
ApoA-1	Apolipoprotein A-1
ApoB	Apolipoprotein B
ASCVD	Atherosclerotic Cardiovascular Disease
AST	Aspartate Aminotransferase
ATC	Anatomical Therapeutic Chemical classification system
BILI	Total Bilirubin
BMI	Body Mass Index
CI	Confidence Interval
COVID-19	Coronavirus Disease 2019
CRS	Case Retrieval Strategy
CSR	Clinical Study Report
DBL	Database Lock
DBP	Diastolic Blood Pressure
ECG	Electrocardiogram
eGFR	Estimated Glomerular Filtration Rate
EOC	End of Core Part
FAS	Full Analysis Set
GCP	Good Clinical Practice
HbA1c	Glycated hemoglobin (hemoglobin A1c)
HDL-C	High-Density Lipoprotein Cholesterol
ICF	Informed Consent Form
IRT	Interactive Response Technology
ITT	Intent-To-Treat
LDL-C	Low-Density Lipoprotein Cholesterol
LFT	Liver Function Test
LLQ	Lower Limit of Quantification
LLT	Lipid Lowering Therapy
Lp(a)	Lipoprotein (a)
MACE	Major Adverse Cardiovascular Event
MAR	Missing-at-Random
MedDRA	Medical Dictionary for Drug Regulatory Affairs
non-HDL-C	non-High-Density Lipoprotein Cholesterol
PCSK9	Proprotein Convertase Subtilisin/Kexin type 9
PD	Pharmacodynamics
PDS	Programming Datasets Specifications

PK	Pharmacokinetics
PMM	Pattern-Mixture Model
PT	Preferred Term
Q1	First Quartile
Q3	Third Quartile
RAS	Randomized Analysis Set
RDO	Retrieved Drop Out
SAE	Serious Adverse Event
SAF	Safety Analysis Set
SAP	Statistical Analysis Plan
SAS	Statistical Analysis System
SBP	Systolic Blood Pressure
s.c.	subcutaneous(ly)
SCR	Screened Set
SD	Standard Deviation
SOC	System Organ Class
TC	Total Cholesterol
TEAE	Treatment-Emergent Adverse Event
TESAE	Treatment-Emergent Serious Adverse Event
ULN	Upper Limit of Normal

## 1 Introduction

This document contains a detailed statistical analysis plan to describe the implementation of the statistical analysis planned in Section 9 of the CKJX839D12305 study protocol version 00 and to support the completion of both the core part clinical study report (CSR) and the Final CSR for the study CKJX839D12305.

The core part analyses will be conducted after the core part database lock (DBL), when all randomized participants have completed the Day 180 visit (or have discontinued from the study). The results from the core part analyses will be summarized in the core part CSR.

[figure not shown]
The final analyses will be conducted when the trial ended. The results from final analyses will be summarized in the final CSR.

### 1.1 Study design

This study is designed as a randomized, double-blind, multi-center phase 3 trial, with a placebo-controlled period and an open label treatment period, to evaluate the efficacy and safety of inclisiran sodium 300mg s.c. in participants aged 18~75 years with low or moderate ASCVD risk and fasting low-density lipoprotein cholesterol (LDL-C) value of  $\geq 130$  mg/dL but  $< 190$  mg/dL who are not on any lipid lowering therapy.

The study design is depicted in [Figure 1-1](#). The study consists of 3 parts:

- **Screening:** a screening period of up to 14 days for all participants
- **Core Part:** a double-blind, placebo-controlled treatment period of 180 days in which eligible participants will be randomized 1:1 to receive either inclisiran sodium 300mg s.c. (Inclisiran Group) or matching placebo s.c. (Control Group) on Day 1 and Day 90. The end of core part (EOC) visit will be conducted on Day 180. The database lock for the core part is planned to occur after all randomized participants have completed the EOC visit (or have discontinued from the study before EOC). The primary endpoint analysis will be conducted after the database lock for the core part.
- **Extension Part:** an extended treatment period of 180 days. After all "Core part" study assessments are completed on Day 180, the extension part starts. In the extension, all patients randomized to inclisiran in the core part will continue on inclisiran while patients initially randomized to placebo will transit to inclisiran therapy. The extension part starts from a dose of study treatment on Day 180 (placebo in the inclisiran group and inclisiran for patients originally randomized to the control group). Thereafter, all participants will receive inclisiran sodium 300mg s.c. on Day 270. Treatment on Day 270 will be open-label. Participants and investigators/site staff will remain blinded to the original randomized treatment group assignment (inclisiran vs placebo) until final database lock. The EOS visit (Day 360) will be the last visit of the study.

**Figure 1-1** Study design

1. Participants who discontinue from study treatment should continue to attend the rest of the scheduled visits.
2. Participants randomized to Inclisiran Group will be treated with inclisiran sodium 300mg s.c. on Day 1 and Day 90 and Day 270, and with matching placebo s.c. on Day 180. Participants randomized to Control Group will be treated with matching placebo s.c. on Day 1 and Day 90, and with inclisiran sodium 300mg on Day 180 and Day 270.
3. The end of core part visit. The database lock for the core part is planned to occur after all randomized participants have completed the EOC visit (or have discontinued from the study before EOC). The primary endpoint analysis will be conducted after the database lock for the core part.
4. Participants who discontinue from study should be scheduled for an Early Exit visit if they agree. This Early Exit visit is suggested to be scheduled at least 30 days after last injection. If not possible, to set an Early Exit visit as soon as possible is also acceptable.

On Day 1 (Baseline), approximately 200 eligible participants who meet all inclusion and not meet any exclusion criteria will be randomized 1:1 to Inclisiran Group and Control Group. Study visits of core part will occur on Day 1 (baseline visit), Day 30, Day 90, Day 150, and Day 180. On Day 1 and Day 90 visits, inclisiran s.c. or placebo s.c. will be administered at the site by a healthcare professional. The primary endpoint will be assessed at Day 150. The EOC visit will be conducted on Day 180.

The extension part starts with a dose on Day 180 after all core part assessments are completed. In order to maintain the blind for the treatment group assignment, participants randomized to Control Group will receive inclisiran, while participants randomized to Inclisiran Group will receive placebo on Day 180. All participants will then receive inclisiran sodium 300 mg on Day 270, which will be the third dose of inclisiran for Inclisiran Group, and the second dose of inclisiran for Control Group. All injections will be administered at the site by a healthcare professional. The EOS visit (Day 360) will be the last visit of the study.

The randomization will not be stratified.

The core part analyses will be conducted when all randomized participants have completed the visit at Day 180 (or have discontinued from the study). The final analyses will be conducted when the trial ended. No interim analyses are planned.

## 1.2 Study objectives, endpoints and estimands

**Table 1-1 Objectives and Endpoints**

Objective(s)	Endpoint(s)
Primary objective(s) 

To demonstrate the superiority of inclisiran as monotherapy, compared to placebo, on mean percentage change from baseline in LDL-C at Day 150, in Chinese adults with low or moderate ASCVD risk and elevated LDL-C who are not on any lipid lowering therapy.

	Endpoint(s) for primary objective(s) 

Percentage change in LDL-C from baseline at Day 150

Secondary objective(s) 

To demonstrate the efficacy of inclisiran as monotherapy, compared to placebo on absolute change from baseline in LDL-C at Day 150.

To demonstrate the efficacy of inclisiran as monotherapy, compared to placebo on percentage and absolute change from baseline in Proprotein Convertase Subtilisin/Kexin type 9 (PCSK9), total cholesterol (TC), high-density lipoprotein (HDL-C), non-high-density lipoprotein cholesterol (non-HDL-C), apolipoprotein B (ApoB), apolipoprotein A-1 (ApoA-1), lipoprotein (a) (Lp(a)) and triglycerides (TG) at Day 150.

To evaluate the effect of inclisiran as monotherapy on percentage and absolute change in LDL-C from baseline at Day 330.

To evaluate the safety and tolerability of inclisiran as monotherapy compared to placebo during core part.

To evaluate the safety and tolerability of inclisiran as monotherapy during extension part.

	Endpoint(s) for secondary objective(s) 

Absolute change in LDL-C from baseline at Day 150

Percentage change from baseline at Day 150 in PCSK9

Absolute change from baseline at Day 150 in PCSK9

Percentage change from baseline at Day 150 in TC, HDL-C, non-HDL-C, ApoB, ApoA-1, Lp(a) and TG

Absolute change from baseline at Day 150 in TC, HDL-C, non-HDL-C, ApoB, ApoA-1, Lp(a) and TG

Percentage change in LDL-C from baseline at Day 330 for inclisiran group

Absolute change in LDL-C from baseline at Day 330 for inclisiran group

Adverse Events (AEs), vital signs and safety laboratory values

Adverse Events (AEs), vital signs and safety laboratory values

